6.4.1. Immunogenicity Assessments

There will be two types of immunogenicity assessments:

- Serum bAb level against SARS-CoV-2 as measured by ELISA specific to the SARS-CoV-2 S protein
- Serum bAb level against SARS-CoV-2 as measured by MSD specific to the SARS-CoV-2 S protein (Part B)
- Serum nAb titer against SARS-CoV-2 as measured by pseudovirus and/or live virus neutralization assays

6.4.2. Analysis of Antibody-Mediated Immunogenicity Endpoints

For each group, the following evaluations will be performed at each time point at which blood samples are collected for immunogenicity (unless otherwise specified):

- GM level of SARS-CoV-2-specific bAb levels with corresponding 95% CI will be provided at each time point. The 95% CIs will be calculated based on the t-distribution of the log-transformed values then back transformed to the original

scale for presentation. GM level and corresponding 95% CI will be plotted at each timepoint. The following descriptive statistics will be also provided at each time point: the number of subjects (n), median, minimum and maximum.

[figure not shown]
- GM fold-rise of SARS-CoV-2-specific bAb levels with corresponding 95% CI will be provided at each post-baseline timepoint over pre-injection baseline at Day 1 for Part A and at OL-Day 1 for Part B. The 95% CIs will be calculated based on the t-distribution of the log-transformed values then back transformed to the original scale for presentation. GM fold-rise and corresponding 95% CI will be plotted at each timepoint. The following descriptive statistics will be also provided at each time point: the number of subjects (n), median, minimum and maximum.
- For VAC65 spike IgG antibody test in Part A and all bAb tests in Part B, proportion of subjects with fold-rise ≥ 2 , fold-rise ≥ 3 , and fold-rise ≥ 4 of serum SARS-CoV-2-specific bAb levels from OL-Day 1 (baseline) at each post-injection time points will be tabulated with 2-sided 95% Clopper-Pearson CIs.
- For VAC65 spike IgG antibody test in Part A and all bAb tests in Part B, proportion of subjects with seroconversion in serum SARS-CoV-2-specific bAb will be tabulated with 2-sided 95% Clopper-Pearson CIs at each post-baseline timepoint. Seroconversion in serum SARS-CoV-2-specific bAb at a participant level is defined as a change of bAb level from below the LLOQ to equal to or above LLOQ, or a 4-times higher titer ratio in participants with pre-existing bAb levels.
- For VAC65 spike IgG antibody test in Part A and all bAb tests in Part B, proportion of subjects with seroresponse for bAb will be tabulated with 2-sided 95% Clopper-Pearson CIs at each post-baseline timepoint.
- GMT of SARS-CoV-2-specific nAb titers with corresponding 95% CI will be provided at each time point using the same method mentioned above.
- GMFR of SARS-CoV-2-specific nAb titers with corresponding 95% CI will be provided at each post-baseline timepoint over pre-injection baseline at Day 1 for Part A and at OL-Day 1 for Part B using the same method mentioned above.
- Proportion of subjects with fold-rise ≥ 2 , fold-rise ≥ 3 , and fold-rise ≥ 4 of serum SARS-CoV-2-specific nAb titers from Day 1 (baseline) at each post-injection time points in Part A and from OL-Day 1 (baseline) at each post-injection time points in Part B will be tabulated with 2-sided 95% Clopper-Pearson CIs.

- Proportion of subjects with seroconversion in serum SARS-CoV-2-specific nAb will be tabulated with 2-sided 95% Clopper-Pearson CIs at each post-baseline timepoint for Part A and Part B respectively. Seroconversion in serum SARS-CoV-2-specific nAb at a participant level is defined as a change of nAb titer from below the LLOQ to equal to or above LLOQ, or a 4-times higher titer ratio in participants with pre-existing nAb titers.
- For Part B, proportion of subjects with seroresponse for nAb will be tabulated with 2-sided 95% Clopper-Pearson CIs at each post-baseline timepoint.
- GM level, GMT and GMFR with corresponding 95% CI will also be evaluated using an ANCOVA model with baseline level/titer as a covariate and age cohort as a factor in the analysis in the overall group. The model will be conducted based on the log-transformed values then back transformed to the original scale for presentation.
- Per the study protocol, if the visit for the second dose (Day 29) is disrupted and cannot be completed at Day 29 (+7 days) as a result of the COVID-19 pandemic (self-quarantine or disruption of clinical site activities following business continuity plans and/or local government mandates for “stay at home” or “shelter in place”), the window may be extended to Day 29 + 21 days. Additional sensitivity analysis of immunogenicity data may be conducted for the above endpoints using the “Adjusted” Per-protocol Set based on the more rigid visit window, -3/+7 for Day 29 visit, as appropriate.
- For Part B booster subjects, summaries and analysis based on pre-injection baseline at Day 1 (pre-dose Day 1 of primary series) will be provided if same assay tests are available across Part A and Part B. For Part B booster subjects, OL-Day 29 immune response after booster will be compared with their own Day 57 immune response of primary series. GMT ratios will be calculated by back transforming the mean of paired differences of antibody titer data on the logarithmic scale between Day 29 post booster and Day 57 of primary series. CIs for the GMT ratio will be based on t-distribution of the log-transformed values then back transformed to the original scale for presentation. Seroresponse rates at OL-Day 29 post boost dose will be compared with their seroresponse rates at Day 57 of primary series. The difference in seroresponse rates and its corresponding 95% CI based on adjusted Wald method (Bonett et al 2012) will be provided.

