6.1. General Considerations

The Schedule of Assessments is provided in the protocol Table 9 for Part A Blinded Phase, Table 11 and Table 12 for Part B Open-Label Phase.

Continuous variables will be summarized using the following descriptive summary statistics: the number of subjects (n), mean, standard deviation (SD), median, minimum (min), and maximum (max).

Categorical variables will be summarized using counts and percentages.

Baseline value, unless specified otherwise, is defined as the most recent non-missing measurement (scheduled or unscheduled) collected before the first dose of study injection. For safety tests (Part B), the baseline is defined as the non-missing measurement collected on OL-Day 1 and before the first dose of study injection in Part B. For immunogenicity tests (Part A) and nasal swab tests, the baseline is defined as the most recent non-missing measurement (scheduled or unscheduled) collected before or on the date of first dose of study injection (Day 1). For immunogenicity tests (Part B) the baseline is defined as the non-missing measurement collected in Part B and before or on the date of first dose of injection in Part B (OL-Day 1).

For the summary statistics of all numerical variables unless otherwise specified, the display precision will follow programming standards. Please see [Appendix A](#) for variable display standards.

When count data are presented, the percentage will be suppressed when the count is zero in order to draw attention to the non-zero counts. A row denoted “Missing” will be included in count tabulations where specified on the shells to account for dropouts and missing values. The denominator for all percentages will be the number of subjects in that age cohort and vaccination group within the analysis set of interest, unless otherwise specified.

Study day relative to the first injection in Part A will be calculated as below:

- a) study day prior to the first injection will be calculated as: date of assessment/event – date of the first injection in Part A;
- b) study day on or after the date of the first injection in Part A will be calculated as: date of assessment/event – date of the first injection in Part A + 1;

Study day relative to the first injection in Part B will be calculated as below:

- a) study day prior to the first injection in Part B will be calculated as: date of assessment/event – date of the first injection in Part B;

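### SAP 6.4.2 names OL-Day 1 as the only baseline for the binding-antibody fold-rise proportions, including those for the Part A VAC65 test, against the Day 1 baseline used for Part A elsewhere in the SAP

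*SAP*

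**What the plan says.** All references are to the SAP for Parts A and B unless stated otherwise.

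- **The bullet at issue (6.4.2).** Its scope is explicit: "For VAC65 spike IgG antibody test in Part A and all bAb tests in Part B, proportion of subjects with fold-rise" thresholds of 2, 3 and 4. Its baseline is "serum SARS-CoV-2-specific bAb levels from OL-Day 1 (baseline) at each post-injection time points". No separate baseline is given for Part A.
- **bAb GMFR (6.4.2, an earlier bullet in the same list).** The fold-rise is taken "at each post-baseline timepoint over pre-injection baseline at Day 1 for Part A and at OL-Day 1 for Part B".
- **nAb fold-rise proportions (6.4.2, the parallel bullet).** These are computed on "nAb titers from Day 1 (baseline) at each post-injection time points in Part A", with OL-Day 1 reserved for Part B.
- **General baseline definition (6.1).** The paragraph opens "Baseline value, unless specified otherwise, is defined as the most recent non-missing measurement" before the first injection. A separate sentence sets the Part A immunogenicity baseline as the latest value on or before the date of the first injection, labelled Day 1. Another sets the Part B baseline at OL-Day 1.
- **Part A Full Analysis Set for bAb (5.5).** Membership requires a Day 1 bAb value. The Part A bAb Per-Protocol Set (5.6) is drawn from it.
- **Precedence (Section 1).** Where SAP and protocol methods differ, the SAP governs. Section 7, which lists changes from the protocol, does not mention this baseline.

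**The concern.** A fold-rise proportion is meant to show how many participants rose from their pre-vaccination level. In Part A only Day 1 is a pre-vaccination sample. OL-Day 1 is collected when the participant moves to Part B, after all the Part A injections that participant received. A ratio of a Part A visit to OL-Day 1 compares an earlier sample with a later one and does not measure a rise from baseline.

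The bullet names Part A and states a baseline, so this is a stated rule that is wrong for Part A and not a missing detail. VAC65 is the only test listed under bAb by ELISA in SAP Table 3, and bAb by ELISA is the Part A primary immunogenicity endpoint (3.1.2), so the affected table concerns the main Part A assay. The distortion would also differ between arms: mRNA-1273 recipients would be divided by a post-vaccination level, whereas uninfected placebo recipients would be expected to have OL-Day 1 levels near Day 1.

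**Working it through.** The documents report no figure that depends on this baseline, so there is none to reproduce. The check is a comparison of texts, followed by an illustration with assumed values.

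**1. Baselines side by side for Part A**

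| Place | Part A baseline |
|---|---|
| SAP 6.1, immunogenicity tests | Day 1 |
| SAP 5.5, FAS for bAb | Day 1 |
| SAP 6.4.2, bAb GMFR | Day 1 |
| SAP 6.4.2, nAb fold-rise proportions | Day 1 |
| Protocol synopsis, bAb GMFR | Day 1 |
| SAP 6.4.2, bAb fold-rise proportions | OL-Day 1 |

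**2. Timing.** In SAP Appendix B, Table 4, the last Part A immunogenicity window (Day 394) closes before the Participant Decision Visit. Protocol Tables 11 and 12 place OL-Day 1 at that visit. OL-Day 1 therefore follows every Part A sample.

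**3. Effect of a literal reading.** For one participant:

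fold rise over OL-Day 1 = (visit level / Day 1 level) ÷ (OL-Day 1 level / Day 1 level)

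The intended fold rise is divided by however much the OL-Day 1 level still exceeds Day 1.

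Illustration with assumed levels in LLOQ units: Day 1 = 0.5 (the SAP's substitution for values below LLOQ), Day 29 = 20, Day 57 = 100, Day 209 = 40, OL-Day 1 = 30.

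| Visit | Over Day 1 | Over OL-Day 1 |
|---|---|---|
| Day 29 | 20/0.5 = 40 | 20/30 = 0.67 |
| Day 57 | 100/0.5 = 200 | 100/30 = 3.33 |
| Day 209 | 40/0.5 = 80 | 40/30 = 1.33 |

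All three visits pass the 4-fold threshold over Day 1, and none passes it over OL-Day 1.

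**4. Range for the Day 57 proportion at the 4-fold threshold.** Assume a Day 57 geometric mean of 100 × LLOQ, a decline from Day 57 to OL-Day 1 by a factor w, and a normal log10 ratio with SD s. Then P(fold rise ≥ 4 over OL-Day 1) = 1 − Φ[(log10 4 − log10 w)/s]. For Day 1, w is replaced by 100/0.5 = 200.

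| w | s = 0.2 | s = 0.4 |
|---|---|---|
| 1 | 0.1% | 6.6% |
| 2 | 6.6% | 22.6% |
| 3 | 26.6% | 37.7% |
| 5 | 68.6% | 59.6% |
| 10 | 97.7% | 84.0% |
| Day 1 baseline | 100.0% | 100.0% |

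Under a literal reading the proportion reflects how far the antibody has waned by OL-Day 1. Over this assumed range the answer runs from almost none to almost all participants, so the documents cannot fix a size.

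**5. Missing results.** A participant who left before Part B has no OL-Day 1 value and no Part A result under the bullet, even with a complete set of Part A samples.

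**The case against.** The strongest reply is that this is a drafting slip whose intended meaning is plain. The Part A sentence in SAP 6.1 fixes Day 1, the Part A bAb analysis sets select participants for having a Day 1 value, the visit-window table lists the two baselines separately, and the neighbouring bullets use Day 1. A baseline drawn after all the visits it is compared with is unlikely to have been chosen. That reply stands as to intent. It does not correct the bullet: no other text does so, the SAP 6.1 paragraph opens by allowing exceptions, and the protocol cannot override the SAP.

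A reader might infer that the Part A primary immunogenicity results are compromised. The documents do not support that. The planned summaries of the primary bAb endpoint are the geometric mean and GMFR. The geometric mean needs no baseline, and the GMFR uses Day 1. The protocol specifies the 2-, 3- and 4-fold proportions for nAb, so the bAb versions are a descriptive SAP addition. The seroconversion and seroresponse bullets do not carry the OL-Day 1 phrase. The study has no hypothesis test.

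A reader might also infer that issued Part A tables are wrong. That is not shown either. SAP version 5.0 says that the Day 57 report and the End of Part A addendum were already final, and nothing shows which baseline was programmed. The planned timing of the Day 57 analysis, with sites blinded until Part B began, suggests that OL-Day 1 samples may not have existed when it was run. The documents do not date that analysis, so this remains an inference.

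**Conclusion.** The point holds as a contradiction within the SAP. For the Part A VAC65 fold-rise proportions, Section 6.4.2 states a baseline that conflicts with every other Part A baseline statement and would give wrong proportions if programmed as written. Where OL-Day 1 exceeds Day 1, as would be expected in most mRNA-1273 recipients, the error understates the rise.

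It is minor. It reaches three descriptive proportions for one assay in a part of the study already reported, and Day 1 was very probably intended. The illustration rests entirely on assumed titers, waning and SD; it shows that the effect could be large or small and does not estimate it. The open question is factual: which baseline did the finalized Part A bAb fold-rise tables use? If OL-Day 1, they need correction. If Day 1, the SAP misdescribes what was done.

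**What to change.** Reword the bullet so that it takes Day 1 as baseline for each post-injection time point in Part A and OL-Day 1 for each post-injection time point in Part B, using the construction already in the parallel nAb bullet. Then check the program or table footnotes behind the issued Part A bAb fold-rise tables, in the Day 57 report and the End of Part A addendum, confirm that Day 1 was used, and correct the tables if it was not.

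The cost is one phrase in the SAP and one check of existing output. Rerunning the tables is needed only if the check fails, and requires no new data.

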6.5. Exploratory Analysis

6.5.1. Exploratory Analysis of Immunogenicity

The below exploratory analyses of immunogenicity may be performed:

6.5.2. Nasopharyngeal Swab Assessments

Nasopharyngeal swab samples will be collected for SARS-CoV-2 testing. The number and percentage of subjects with detected and not detected will be summarized at each visit by age cohort and vaccination group as defined in [Section 6.1](#) for Part A and Part B separately.

6.5.3. SARS-CoV-2 Exposure and Symptoms

SARS-CoV-2 reported exposure history and symptoms assessment will be assessed during the study.

The number and percentage of subjects who had close contact with a person with SARS-CoV-2 infection or COVID-19, reasons for exposure, subjects with any symptoms of potential COVID-19, and subjects with each symptoms will be presented by visit, age cohort, and vaccination group as defined in [Section 6.1](#). Descriptive statistics will be provided for length of exposure in days and time from exposure to first symptom by age cohort and vaccination group.

In addition, the following listings will be provided for subjects infected by SARS-CoV-2:

- Serum bAb level against SARS-CoV-2
- Serum nAb titer against SARS-CoV-2
- Solicited ARs
- Unsolicited AEs

6.6. Planned Analyses

6.6.1. Primary Study Analysis for Blinded Part A Only

A primary analysis of safety and immunogenicity data will be performed after participants have completed Day 57 study procedures. This primary analysis may be performed when all participants in Cohort 1 and the Cohort 2 sentinel group have completed Day 57 study procedures and/or when all participants in Cohort 1 and Cohort 2 have completed Day 57 study procedures. All data relevant to the primary study analysis through Day 57 will be cleaned (as clean as possible) and locked. A limited number of Sponsor and clinical research organization (CRO) personnel will be unblinded to perform the primary study analysis and prepare a final CSR.

An independent, unblinded statistics team will carry out the primary analysis. The unblinded statistics team will not be involved in either study design or the regular study conduct. The study site staff, investigators, study monitors, and participants will remain blinded until the initiation of Open-Label Part B.

6.6.2. Analysis at End of Blinded Part A Only

An analysis of safety and immunogenicity data will be performed after all participants have completed Part A of the study. All data collected in Part A of the study will be cleaned (ie, data that are as clean as possible) and locked and a report may be generated as needed.

6.6.3. Interim Analyses for Open-Label Part B Only

Interim analyses of the safety and immunogenicity data may be performed after participants have completed the OL-Day 29 and/or the OL-Day 57 study procedures. This analysis may be performed when all participants have completed OL-Day 29 and/or OL-Day 57 study procedures, or on a subset of participants who received a single booster dose at OL-Day 1 when they have completed OL-Day 29 and/or OL-Day 57 study procedures. All data collected in Part B of the study will be cleaned (ie, data that are as clean as possible) and locked and a report may be generated as needed. Results of this analysis may be presented in a CSR.

6.6.4. Additional Study Analyses

Additional analyses may be performed to support regulatory request as appropriate.

6.6.5. Final Analysis at End of Part B

The final analysis of all endpoints for Open-Label Part B will be performed after all participants have completed OL-M6 and OL-M7 respectively (Open-Label Part B) study procedures and after the database is cleaned and locked. All data collected from the initiation of Part B to End of Part B will be included in this analysis. Results of this analysis will be presented in an end of study CSR, including individual listings.

6.7. Safety Monitoring Committee (SMC) Review

There is one planned safety review for Part A blinded Phase by the Safety Monitoring Committee (SMC) consists of external experts. Specific details regarding responsibilities and governance, including the roles and responsibilities of the various members and the SPONSOR and designated CRO study team; and requirements for the proper documentation of SMC minutes will be described in a separate charter that will be reviewed and approved by the SMC.

7. Changes from Planned Analyses in Protocol

Section	Planned Analysis in Protocol	Analysis in SAP
6.1 General Consideration	Antibody values reported as below the limit of detection or LLOQ will be replaced by $0.5 \times$ limit of detection or $0.5 \times$ LLOQ.	Antibody values reported as below LLOQ will be replaced by $0.5 \times$ LLOQ.
6.4 Immunogenicity Analysis	Seroconversion at a participant level is defined as a change of nAb titer from below the limit of detection or LLOQ to equal to or above limit of detection or LLOQ (respectively), or a 4-times or higher titer ratio in participants with pre-existing nAb titers.	Seroconversion at a participant level is defined as a change of nAb titer from below the LLOQ to equal to or above LLOQ (respectively), or a 4-times or higher titer ratio in participants with pre-existing nAb titers.

8. References

Department of Health and Human Services (DHHS), Food and Drug Administration, Center for Biologics Evaluation and Research (US). Guidance for industry: Toxicity grading scale for healthy adult and adolescent volunteers enrolled in preventative vaccine clinical trials. September 2007 [cited 2019 Apr 10] [10 screens]. Available from:

<https://www.fda.gov/downloads/BiologicsBloodVaccines/GuidanceComplianceRegulatoryInformation/Guidances/Vaccines/ucm091977.pdf>.

9. List of Appendices

9.1. Appendix A Standards for Safety and Immunogenicity Variable Display in TFLs

Continuous Variables: The precision for continuous variables will be based on the precision of the data itself. The mean and median will be presented to one decimal place more than the original results; the SD will be presented to two decimal places more than the original results; the minimum and maximum will be presented to the same precision as the original results.

Categorical Variables: Percentages will be presented to 1 decimal place.

9.2. Appendix B Analysis Visit Windows for Safety and Immunogenicity Analysis

Safety and Immunogenicity Analysis will be summarized using the following analysis visit window for post injection assessments:

Step 1: If the safety and immunogenicity assessments are collected at scheduled visit, i.e. nominal scheduled visit, the data collected at scheduled visit will be used.

Step 2: If the safety and immunogenicity assessments are not collected at the scheduled visit, assessments collected at unscheduled visit will be used using the analysis visit windows described in [Table 4](#) below.

If a subject has multiple assessments within the same analysis visit, the following rule will be used:

- If multiple assessments occur within a given analysis visit, the assessment closest to the target study day will be used.
- If there are 2 or more assessments equal distance to the target study day, the last assessment will be used.

Table 4 Visit Window

Visit	Target Study Day	Visit Window in Study Day
Labs		
Day 29 (Month 1)	29 (Date of Second Injection)	[2, 43]
Day 57 (Month 2)	57	≥44 and prior to Participant Decision Visit

Nasal Swabs for SARS-CoV-2		
Baseline	1 (Date of First Injection)	≤ 1
Day 29 (Month 1)	29 (Date of Second Injection)	[2, 43]
Day 57 (Month 2)	57	[44, 70]
Day 71 or Beyond	71	≥ 71 and prior to Participant Decision Visit
Baseline (OL-Day 1)	1 (Date of First Injection on OL-Day 1) relative to OL-Day 1	≤ 1 and VISIT is OL-Day 1
OL-Day 29	29 (Date of Second Injection in Part B) relative to OL-Day 1	[2, 43]
OL-Day 57	57 relative to OL-Day 1	[44, 70]
OL-Day 71 or Beyond	71 relative to OL-Day 1	≥ 71
Vital Signs		
Day 8	8	[2, 11]
Day 15	15	[12, 22]
Day 29 (Month 1)	29 (Date of Second Injection)	[23, 32]
Day 36	36	[33, 39]
Day 43	43	[40, 50]
Day 57 (Month 2)	57	[51, 133]
Day 209 (Month 7)	209	[134, 301]
Day 394 (Month 13)	394	≥ 302 and prior to Participant Decision Visit
Baseline (OL-Day 1)	1 (Date of First Injection on OL-Day 1) relative to OL-Day 1	≤ 1 and VISIT is OL-Day 1
OL-Day 29	29 (Date of Second Injection in Part B) relative to OL-Day 1	[2, 43]
OL-Day 57 for subjects receiving 2 doses in Part B	57 relative to OL-Day 1	[44, 133]
OL-Day 209 for subjects receiving 2 doses in Part B	209 relative to OL-Day 1	≥ 134
OL-Day 57 for subjects receiving 1 dose in Part B	57 relative to OL-Day 1	[44, 119]

OL-Day 181 for subjects receiving 1 dose in Part B	181 relative to OL-Day 1	≥ 120
Immunogenicity		
Baseline	1 (Date of First Injection)	≤ 1
Day 15	15	[2, 22]
Day 29 (Month 1)	29 (Date of Second Injection)	[23, 36]
Day 43	43	[37, 50]
Day 57 (Month 2)	57	[51, 133]
Day 209 (Month 7)	209	[134, 301]
Day 394 (Month 13)	394	≥ 302 and prior to Participant Decision Visit
Baseline (OL-Day 1)	1 (Date of First Injection on OL-Day 1) relative to OL-Day 1	≤ 1 and VISIT is OL-Day 1
OL-Day 8	8 relative to OL-Day 1	[2, 11]
OL-Day 15	15 relative to OL-Day 1	[12, 22]
OL-Day 29 (Month 1)	29 (Date of Second Injection) relative to OL-Day 1	[23, 43]
OL-Day 57 for subjects receiving 2 doses in Part B	57 relative to OL-Day 1	[44, 133]
OL-Day 209 for subjects receiving 2 doses in Part B	209 relative to OL-Day 1	≥ 134
OL-Day 57 for subjects receiving 1 dose in Part B	57 relative to OL-Day 1	[44, 119]
OL-Day 181 for subjects receiving 1 dose in Part B	181 relative to OL-Day 1	≥ 120

9.3. Appendix C Imputation Rules for Missing Prior/Concomitant Medications and Non-Study Vaccinations

Imputation rules for missing or partial medication start/stop dates are defined below:

1. Missing or partial medication start date:
 - If only DAY is missing, use the first day of the month, unless:
 - The CM end date is after the date of first injection or is missing AND the start month and year of the CM coincide with the start month and year of the first injection. In this case, use the date of first injection
 - If DAY and Month are both missing, use the first day of the year, unless:
 - The CM end date is after the date of first injection or is missing AND the start year of the CM coincide with the start year of the first injection. In this case, use the date of first injection
 - If DAY, Month and Year are all missing, the date will not be imputed, but the medication will be treated as though it began prior to the first injection for purposes of determining if status as prior or concomitant.
2. Missing or partial medication stop date:
 - If only DAY is missing, use the earliest date of (last day of the month, study completion, discontinuation from the study, or death).
 - If DAY and Month are both missing, use the earliest date of (last day of the year, study completion, discontinuation from the study, or death).
 - If DAY, Month and Year are all missing, the date will not be imputed, but the medication will be flagged as a continuing medication.

In summary, the prior, concomitant or post categorization of a medication is described in [Table 5](#) below.

Table 5 Prior, Concomitant, and Post Categorization of a Medication

Medication Start Date	Medication Stop Date		
	< First Dose Date of Study Injection	≥ First Dose Date and ≤ End Date of Last Study Injection in each Part + 27 days	> 27 Days After Last Injection in each Part [2]
< First dose date of study vaccination [1]	P	PC	PCA
≥ First dose date and ≤ 27 days after last injection in each Part	-	C	CA
> 27 days after last injection in each Part	-	-	A

A: Post; C: Concomitant; P: Prior

[1] includes medications with completely missing start date

[2] includes medications with completely missing end date

